Skinner and Allen (1982) found that clinicians treating patients with Alcohol Dependence often find that their patients report symptoms and signs that are very different from what the textbooks describe.

Despite this, certain elements have been grouped as essential in ADS. These include:

- Narrowing in the repertoire (internal and external cues to drink) of drinking behaviour
- Salience of drink-seeking behaviour
- Increased tolerance to alcohol
- Repeated withdrawal symptoms
- Repeated relief from/avoidance of withdrawal symptoms by drinking
- A subjective awareness of a compulsion to drink
- Relapse of the syndrome after a period of abstinence

Moreover, these elements vary in the degree to which they are present or experienced, and thus the syndrome has a *range of severity*. Further, they characterise dimensions along which clinicians can organise the information obtained from the patient (2).

Craving

Craving is “aversive, confusing, intrusive, frustrating, and exasperating”. It can control thoughts and tends to keep people awake at night, even causing irrational words and actions from people who might otherwise be reasonable.

A number of addiction theorists hypothesise that *craving* plays an important role in both acquisition and maintenance of dependence on a drug, like alcohol.

Tiffany and Conklin (2000) theorised that craving has two prominent features:

1. It tends to be highly situational i.e. specifically and easily triggered by stimuli that have earlier association with use of alcohol.
2. Its experience can persist beyond the point of abstinence/cessation of drinking. (3)

Coping with Craving

Since craving has been described as aversive, an obvious corollary is that individuals who experience craving will find some ways to *cope* with the craving.

Coping refers to “behaviour that protects people from being harmed by problematic [social] experience”. It consists of behaviour(s) that mediate the impact of issues like alcohol withdrawal, stress, societal restrictions, aggression, etc. on individuals.

Pearlin and Schooler (1978) theorise that coping behaviour(s) perform their protective functions in one of three possible ways –

1. Removing or changing conditions that give rise to the problem
2. “Perceptually controlling the meaning” of an experience in a way that neutralises or diffuses the aspect of the experience that is problematic.
3. Ensuring that the emotional consequences of the problem are kept within “manageable bounds”. (4)

According to Frydenberg & Lewis (2011), coping strategies can be both Productive and Unproductive.

- Productive Coping Strategies – These entail dealing with the problem, and finding ways to protect self from the psychologically damaging consequences of a particular emotion/situation/event, while simultaneously making the attempt “to remain physically active and socially connected”.

Some examples include seeking social support, focussing on solving the problem, relaxation techniques, physical recreational activities like sports, relaxing diversions like art and dance, acceptance, and seeking professional help.

- Negative Coping Strategies – These generally encompass the use of *avoidance* strategies. These are usually associated with reduced ability or lack of ability to cope with stressors.

Some examples include worrying, wishful thinking, ignoring the problem, withdrawing from social circle, self-blame, and acting out. (5)

Jacobsen's Progressive Muscle Relaxation (JPMR)

“An anxious mind cannot exist in a relaxed body”. This quote by [name], is the basis for JPMR. (6)

It is the therapeutic technique of choice for use in stress and anxiety management. JPMR was created such that it would eventually be something that the practitioner [i.e. patient] would be able to automatically and unconsciously monitor and release unwanted tension.

The technique includes the “Tension–Release” cycle (e.g. make a tight fist and then release) which has been combined with a focus on breathing. It is aimed at getting in touch with the individual's tension and the body's response, and then letting it go in a controlled manner.

Freeman (2001) suggests that PMR and other muscle-based relaxation variations convey health benefits in three ways:

1. Utilizing the effects of PMR to manipulate autonomic responses
2. Increases or activates the production of opiates
3. Promotes optimal immune function

The PMR method - strong record of clinical efficacy, acknowledged as standard strategy for a number of somatic states, including anxiety and stress. (7)

Music

Music is a “dynamic medium” that is used for inspiration, and relaxation, often on a daily basis, by many people. With this as the basis, music now plays a larger role in health and healing. Music therapy or music-based interventions are an alternative treatment route

focussed on helping patients deal with physical, emotional, and cognitive problems. It aims to enhance social or interpersonal, affective, cognitive, and behavioural functioning.

Research also shows that music is also effective at reducing muscle tension and anxiety and promotes relaxation, verbalisation, group cohesiveness and interpersonal relationships (8)

In the theory of music literature, the core assumption is on the *functions* of music. Music is generally composed or played for emotional expression. It is used to contain behaviours, and trigger cognitions. A 2007 study with adolescents found that apart from entertainment, healthy individuals used music to relax, distract themselves from certain emotions, or even to discharge these emotions, energise themselves, offer comfort or solace. Music is found to provoke sensory images within individuals - the strength of which differs from person to person.

Music also works in enabling people to sense, recognise, and express inner physical, psychological, emotional, or cognitive motions that play a role in their daily lives. The creation of music leads to expression and containment of the emotions at the same time. This is termed the *containing power of music*.

Society often frowns upon the expression of certain emotions like anger through aggression. Music has the power to let people experience emotion and express it without acting on it in reality.

Thus, music therapy works by applying the containing power of music and its psycho-bio-social aspects in a systematic manner to influence people (9)

Studies have demonstrated neurological pathways that imply application of music therapy in individuals with substance abuse problems, since, music stimulates brain processes that affect the production of certain endorphins in receptors (DRD2). The long-term use of substances severely impairs and/or damages these pathways. (8)

In a 2001 study by Daveson and Edwards, female inmates in jail reported that felt more relaxed, less stressed, and could express themselves better after 12 music therapy sessions. Patients also indicate reduction in anger, stress and frustration. Thus, research has indicated that music therapy or music-based interventions can help to move coping skills from *mainly aggressive* behaviour to *general behaviour* (10)

Review of Literature

Alcohol and Stress

(In the literature, stress is used as an umbrella term for anxiety, tension, stress, defensiveness, and associated feelings.)

Fox et al (2007) conducted a study with 20 treatment seeking ADS patients using guided imagery to imagine a “recent personal stressor, personal alcohol cue-related stressor, and a neutral imagery situation” over 3 sessions, one per session in random order. Exposure to stress and to alcohol cues each produced significant increases in alcohol craving, anxiety, and negative emotions and decreases in positive emotions.

Stress-induced alcohol craving was significantly correlated with increases in sadness, anger, and anxiety ratings, but alcohol cue-induced craving was associated with decreases in positive affect (joy and neutral relaxed state) and increases in anxiety and fear ratings. (11)

Duka et al. (2006) found in patients with multiple episodes of withdrawals from alcohol, associated craving, and anxiety. (12)

In a similar study conducted in 2000 by Sinha et al., it was observed that there were significant increases in the level of cocaine and alcohol craving with stress and drug cues imagery but not with neutral-relaxing imagery.

They also found that similar increases in subjective anxiety, heart rate and salivary cortisol levels are produced by stress and drug cues.

It was also found that there are significant increases in ratings for negative emotions and decreases in ratings for positive emotion for stress and drug cue conditions as compared to the neutral condition. (13)

Alcohol, Stress, and Relapse

In the 2004 meeting of the Research Society on Alcoholic Meeting Symposium, Sinha presented clinical evidence that increased sensitivity to craving increases risk for relapse; stress can cause anxiety like symptoms through craving; and that there is sufficient evidence to conclude that stress is involved in a relapse. (14)

Sinha and Li (2006) found that major factors contributing to high rates of relapse are stress and drug related cues. Further, there is an overlap in the brain areas that process stress and drug cue-induced craving, including in the medial prefrontal cortex, anterior and posterior cingulate cortex, striatal and postular insula regions; and these regions have been associated with craving state and increased susceptibility to relapse. (15)

Craving and Stress

Gruser, Morsen and Flor (2006) conducted a study on the level of craving in 50 problem drinkers, and occasional drinkers. The problem drinkers were found to have higher amount of craving accompanied by increased stress-distress; along with a higher tendency to use inadequate (negative) coping strategies.

Further, craving was found to be a significant predictor of craving. They concluded that there needs to be a focus on alternative coping strategies that would be beneficial in the management of craving. (16)

Dharmadhikari and Sinha (2015) described craving as the *psychic pain of addiction*, and that it was the *obstacle* to abstinence. Craving is what turns drug-taking behaviour into compulsive drug-taking behaviour. (17)

Swift and Stout (1992) found that craving and anxiety stress share many similar attributes, including comparable response to pharmacological agents. In their work with 32

patients who used opioids, they found the highest positive correlation between anxiety and craving. (18)

Coping with Stress and Use of Music

Labbe et al. (2007) hypothesised that listening to relaxing classical music after being exposed to a stressor should result in “significant reductions in anxiety, anger, and sympathetic nervous system arousal, and increased relaxation compared to those who sit in silence or listen to heavy metal music”. Their results indicated that listening to classical music, after exposure to a stressor, significantly reduces negative emotional states and physiological arousal compared to listening to heavy metal music or sitting in silence. (19)

A meta-analysis of 22 studies by Pelletier (2004), showed that arousal due to stress is significantly reduced with music and music assisted relaxation techniques. Stress, including anxiety, fear, and tension, was found to significantly influenced by music, and strong positive correlations were observed with increased relaxation and the playing of music.

The strongest correlations were found with classical, instrumental music without lyrics, and with regular, rhythmic patterns, and no extreme changes (e.g. a beat drop). (20)

In a 2001 study by Knight and Rickard, they exposed 87 participants to a cognitive stressor task, either in presence of classical, instrumental music, or in silence. When the two groups were compared on physiological and subjective (psychological) measures of anxiety, it was found that exposure to music prevented stress induced stress induced physical arousal, and thus music acts as an effective anxiolytic. (21)

Alcohol and Music

Silverman found significant difference in the readiness to change alcohol-use behaviours between patients who were given music-based interventions and verbal therapy. Though not significant, the patients in the music group were also found to have lower craving scores. (22)

Stress and PMR

In 2015, Kaur and Kaur found that PMR was effective in reducing stress levels of patients admitted for alcohol deaddiction, significant at 0.05 level. (23)

In her 2014 study with staff nurses in Vadodara, Patel found significant reduction in stress levels experienced by nurses with the use of Progressive Muscle Relaxation through pre- and post-test measures. (24)

Bommareddi et al. (2014) conducted a study with 30 patients who are living with HIV, 13% of whom had abnormal anxiety, and the rest has the increased stress levels associated with living with HIV. Comparing pre- and post-test measures of stress with the use of PMR, the reduction in stress levels was found to be significant at 0.001 level. (25)

Rationale of the Study

Music is an adaptive, emotion-based coping strategy, and research has shown that music-based interventions have a positive effect on levels of stress, aggression, and frustrations. Since these emotions are also associated with craving, this study aims to find if music will work in a similar manner to help patients deal with craving for alcohol.

The control technique of JPMR is selected based on research evidence that indicates its benefit with the management of stress, anxiety, depression, aggression, and frustration.

Need for the Study

As seen through the review of literature, alcohol craving and stress and correlated with relapse. Further, the use of music has demonstrated significant reduction in the level of stress experienced across various clinical and non-clinical populations.

GAP IN THE KNOWLEDGE

Though there are studies on use of music to cope with cocaine withdrawal, there is no study conducted, especially in the Indian scenario, on the effect of music on coping with craving alcohol.

If the effect is found to be significant, it can create an avenue for further research, and provide a simple, cost-free addition to treatment of patients with ADS.

Methodology

Aim

To compare the effectiveness of music and progressive muscle relaxation on craving alcohol and perceived ability to cope with craving in patients with alcohol dependence syndrome.

Objectives

1. To compare the pre and post-test measures of craving and coping for the two groups (within groups).
2. To check the difference in the pre and post-test measures of craving and coping in the two groups (between groups).
3. To analyse the responses obtained through a Single Question Exit Interview, to understand patients' subjective perception about the music and the muscle relaxation

Hypothesis

1. There is no difference in the effectiveness of music and progressive muscle relaxation on craving alcohol
2. There is no difference in the effectiveness of music and progressive muscle relaxation on perceived ability to cope with craving alcohol.

Sampling

- Size – 10 patients in each group, so a total of 20 patients will be selected.
- Method – Purposive sampling will be used.

- Design – Randomized parallel intervention trial
- Criteria
 - Inclusion criteria
 - Patients with ADS
 - Adults in the age range of 18-60, of either gender
 - Abstinent for at least 1 week
 - Exclusion criteria
 - Any other known psychiatric disorder/severe medical condition
 - Use/abuse of substances other than alcohol and nicotine
 - At risk for self-harm or suicide
 - Drop-out criteria
 - Less than 75% compliance
 - Relapse (defined as a return to drinking behaviour)

The study duration will be 1 year, conducted on patients from Mangalore.

Tools to be used in the study

Three scales will be used in the study, along with a single question exit interview. Further, recorded versions of music and PMR will be used to ensure uniformity in delivery of the intervention.

1. URICA Scale

The University of Rhode Island Change Assessment (URICA) Scale is designed to assess the change readiness of an individual. It acts as a screening tool for assessment of the stage of change a patient with ADS is at, based on Prochaska's Transtheoretical Model of Change.

The scale has been found to have excellent reliability and was a significant predictor of

treatment dropout and retention. The scale also showed moderate reliability as a predictor of patient prognosis. (26,27)

2. *Alcohol Urge Questionnaire (AUQ)*

The AUQ is a self-report measure of craving alcohol, with eight items, with high internal consistency (0.91); and high test-retest reliability of 0.82 after 24 hours; as well as suitable construct validity. (28)

3. *Visual Analogue Scale (VAS)*

The VAS is a line 100mm in length, with both the ends indicating extremes of the construct being assessed. Used generally to assess pain, VAS measures have been found to be reliable and valid measures of a number of constructs as needed. The VAS used here ranges from Completely Unable to Cope and Completely Able to Cope. The patient will indicate their subjective perception of their own ability to cope with craving alcohol.

4. *Single Question Exit Interview (SQI)*

Each patient will be asked a single question during the final debriefing on the last day of the study. The question will be “Please describe your experience with the music/exercise”. Their answers will be recorded verbatim and will be translated from Kannada as needed.

5. *The music*

Based on the reviewed literature, Raga Bhairavi and Ahir Bhairav, played on the flute with no lyrics sung will be used in the study. (20,29–31)

The music will be played to the patients through a speaker, keeping the volume constant across all patients.

6. *The Progressive Muscle Relaxation*

A twenty-minute PMR based on Jacobsen's Progressive Muscle Relaxation was developed and will be recorded in English and Kannada. (32) This will be done to ensure uniformity of delivery of instructions across patients.

Procedure

Ethical approval will be sought from the Institutional Committee. Permission will be sought from the head of the rehabilitation facility, as well as from the treating psychiatrist for each individual patient. Patients will be recruited at random from the rehabilitation centre. After an intake interview to ensure that they meet the required criteria and providing them with all the information regarding the study, informed consent will be attained. They will be allocated to either the music group or PMR group randomly through a sequence generated through the randomizer..

Then, the URICA will be administered to obtain baseline motivation levels on Day 1, followed by AUQ, VAS for Coping. Then the first session of the assigned intervention will be conducted. On subsequent days, further sessions of the intervention will be conducted. AUQ and VAS measurements will be taken on Day 3 and Day 5.

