3. AUQ
4. VAS for Coping
5. Patient Register
6. Record Sheet
7. Randomised list of assigning conditions
8. Permissions for
 - a. URICA
 - b. AUQ
9. Letter of permission from treating psychiatrist

2. URICA – Change Assessment Scale

University of Rhode Island

Change Assessment Scale (URICA) : Alcohol Version

Client ID# _____

Date: ____/____/____

Assessment Point: _____

EACH STATEMENT BELOW DESCRIBES A HOW A PERSON MIGHT FEEL WHEN STARTING THERAPY OR APPROACHING PROBLEMS IN THEIR LIVES. PLEASE INDICATE THE EXTENT TO WHICH YOU TEND TO AGREE OR DISAGREE WITH EACH STATEMENT. IN EACH CASE, MAKE YOUR CHOICE IN TERMS OF HOW YOU FEEL RIGHT NOW, NOT WHAT YOU HAVE FELT IN THE PAST OR WOULD LIKE TO FEEL. FOR ALL STATEMENTS THAT REFER TO YOUR "PROBLEM", ANSWER IN TERMS OF PROBLEMS RELATED TO YOUR DRINKING. THE WORDS "HERE" AND "THIS PLACE" REFER TO YOUR TREATMENT CENTER.

THERE ARE FIVE POSSIBLE RESPONSES TO EACH OF THE ITEMS IN THE QUESTIONNAIRE:

- 1=Strongly Disagree
- 2=Disagree
- 3=Undecided
- 4=Agree
- 5=Strongly Agree

CIRCLE THE NUMBER THAT BEST DESCRIBES HOW MUCH YOU AGREE OR DISAGREE WITH EACH STATEMENT.

	Strongly Disagree	Disagree	Undecided	Agree	Strongly Agree
1) I'm not the problem one. It doesn't make much sense for me to consider changing.	1	2	3	4	5
2) I am finally doing some work on my problem.	1	2	3	4	5
3) I've been thinking that I might want to change something about myself.	1	2	3	4	5
4) At times my problem is difficult, but I'm working on it.	1	2	3	4	5
5) Trying to change is pretty much a waste of time for me because the problem doesn't have to do with me.	1	2	3	4	5
6) I'm hoping that I will be able to understand myself better.	1	2	3	4	5
7) I guess I have faults, but there's nothing that I really need to change.	1	2	3	4	5
8) I am really working hard to change.	1	2	3	4	5
9) I have a problem and I really think I should work on it.	1	2	3	4	5
10) I'm not following through with what I had already changed as well as I had hoped, and I want to prevent a relapse of the problem.	1	2	3	4	5

	Strongly Disagree	Disagree	Undecided	Agree	Strongly Agree
11) Even though I'm not always successful in changing, I am at least working on my problem.	1	2	3	4	5
12) I thought once I had resolved the problem I would be free of it, but sometimes I still find myself struggling with it.	1	2	3	4	5
13) I wish I had more ideas on how to solve my problem.	1	2	3	4	5
14) Maybe someone or something will be able to help me.	1	2	3	4	5

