15) I may need a boost right now to help me maintain the changes I've already made.	1	2	3	4	5
16) I may be part of the problem, but I don't really think I am.	1	2	3	4	5
17) I hope that someone will have some good advice for me.	1	2	3	4	5
18) Anyone can talk about changing; I'm actually doing something about it.	1	2	3	4	5
19) All this talk about psychology is boring. Why can't people just forget about their problems?	1	2	3	4	5
20) I'm struggling to prevent myself from having a relapse of my problem.	1	2	3	4	5
21) It is frustrating, but I feel I might be having a recurrence of a problem I thought I had resolved.	1	2	3	4	5
22) I have worries but so does the next guy. Why spend time thinking about them?	1	2	3	4	5
23) I am actively working on my problem.	1	2	3	4	5
24) After all I had done to try and change my problem, every now and then it comes back to haunt me.	1	2	3	4	5

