3. AUQ

Date of Interview/Examination (MM/DD/YYYY): _____

Listed below are questions that ask about your feelings about drinking. The words "drinking" and "have a drink" refer to having a drink containing alcohol such as beer, wine, or liquor. Please indicate how much you agree or disagree with each of the following statements by selecting one number for each question between STRONGLY DISAGREE and STRONGLY AGREE. The closer you select a number to one end or the other indicates the strength of your disagreement or agreement. Please complete every item. We are interested in how you are thinking or feeling right now as you are filling out the questionnaire.

RIGHT NOW

1. All I want to do now is have a drink.
 - 1 STRONGLY DISAGREE
 - 2
 - 3
 - 4
 - 5
 - 6
 - 7 STRONGLY AGREE

2. I do not need to have a drink now.
 - 1 STRONGLY DISAGREE
 - 2
 - 3
 - 4
 - 5
 - 6
 - 7 STRONGLY AGREE

3. It would be difficult to turn down a drink this minute.
 - 1 STRONGLY DISAGREE
 - 2
 - 3
 - 4
 - 5
 - 6
 - 7 STRONGLY AGREE

4. Having a drink now would make things seem just perfect.
 - 1 STRONGLY DISAGREE
 - 2
 - 3
 - 4
 - 5
 - 6
 - 7 STRONGLY AGREE

5. I want a drink so bad I can almost taste it.
 - 1 STRONGLY DISAGREE
 - 2
 - 3
 - 4
 - 5
 - 6
 - 7 STRONGLY AGREE

6. Nothing would be better than having a drink right now.

- 1 STRONGLY DISAGREE
- 2
- 3
- 4
- 5
- 6
- 7 STRONGLY AGREE

7. If I had the chance to have a drink, I don't think I would drink it.

- 1 STRONGLY DISAGREE
- 2
- 3
- 4
- 5
- 6
- 7 STRONGLY AGREE

8. I crave a drink right now.

- 1 STRONGLY DISAGREE
- 2
- 3
- 4
- 5
- 6
- 7 STRONGLY AGREE

4. VAS for Coping

5. Directory

Patient

S. No.

Hospital No.

Study Code:

Initials:

D.O.B:

Gender:

Education:

Occupation:

SES:

Marital Status:

City of Residence:

Mobile:

Email:

Caregiver

Name:

Relation:

Education:

Mobile:

Email:

(An Excel sheet will be used to record this information)

6. Record Sheet

	A	B	C	D	E	F	G	H	I	J	K	L	M	N	O	P
1	Study Code				Intake/Day One					Day Three					Day Five	
2		Date	AUQ		VAS	Comments, if any	Date	AUQ		VAS	Comments, if any	Date	AUQ		VAS	Comments, if any
3																
4																
5																
6																
7																
8																
9																
10																
11																
12																
13																
14																
15																
16																
17																
18																
19																
20																

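### On Day 1 only, the URICA is given directly before the AUQ and VAS, so the pre and post scores in the within-arm paired t tests are taken under different conditions

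*Combined protocol and SAP*

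**What the plan says.** The Procedure section fixes the Day 1 sequence: "Then, the URICA will be administered to obtain baseline motivation levels on Day 1, followed by AUQ, VAS for Coping". Treatment comes next: "Then the first session of the assigned intervention will be conducted". For the later visits it says: "AUQ and VAS measurements will be taken on Day 3 and Day 5". No URICA is named for those days, and the record sheet (Appendix 6) has only AUQ and VAS columns at each of the three visits.

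The URICA form in Appendix 2 tells the patient to "ANSWER IN TERMS OF PROBLEMS RELATED TO YOUR DRINKING" and runs to 24 items, the last being "24) After all I had done to try and change my problem, every now and then it comes back to haunt me". The AUQ form in Appendix 3 asks about the moment of completion: "We are interested in how you are thinking or feeling right now as you are filling out the questionnaire".

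The first objective is "To compare the pre and post-test measures of craving and coping for the two groups (within groups"). The Analysis of Data section assigns it a paired t test, and assigns the comparison of the two groups an unpaired t test on post-test scores.

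**The concern.** A paired t test of pre against post assumes that the two scores differ only by what happened between them. Here they also differ in what came just before them. At baseline, the patient has just rated two dozen statements about the drinking problem. At the post-tests the patient has not, as far as the schedule shows. No gap, counterbalancing or matching step is described.

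The protocol's own account of craving makes this more than a formality. In the Craving section it says: "It tends to be highly situational i.e. specifically and easily triggered by stimuli that have earlier association with use of alcohol". The AUQ measures a momentary state, so it is the kind of score that could respond to what precedes it.

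At stake is Objective 1. A baseline pushed towards more craving or less perceived coping would make both music and PMR look effective with no true effect. A baseline pushed the other way would hide real improvement. Both arms share the order and there is no untreated arm, so the data could not reveal either case.

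**Working it through.** **Schedule**

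| | Day 1 | Day 3 and Day 5 |
|---|---|---|
| Questionnaire directly before AUQ and VAS | URICA, 24 items | none named |
| AUQ and VAS relative to that day's session | before | not stated |
| Use in the paired t test | pre | post |

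**Is there a plan figure to reproduce?** No. The documents give no significance level, SD, effect size or calculation behind the 10 patients per group.

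**Inputs for an illustration**
- n = 10 per arm (Sampling).
- Pre/post correlation r. The upper value is 0.82, the AUQ 24-hour retest reliability in the tools section. That interval is shorter than Day 1 to Day 5, so r = 0.6 is added as an assumed lower value.
- Two-sided 5% level (assumed).
- No true change, and a Day 1 shift of s SD caused by order (assumed; not in the documents).

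**Formulas**, with the AUQ SD set to 1 on both days
- SD of the difference = √(2(1 − r)). For r = 0.82: √0.36 = 0.600. For r = 0.6: √0.80 = 0.894.
- Noncentrality = s × √10 / SD of the difference. For s = 0.2 and r = 0.82: 0.2 × 3.162 / 0.600 = 1.054.
- Rejection rate = probability that a noncentral t on 9 df falls outside ±2.262.

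| Assumed shift s | r = 0.6 | r = 0.82 |
|---|---|---|
| 0 | 5.0% | 5.0% |
| 0.05 SD | 5.3% | 5.6% |
| 0.1 SD | 6.2% | 7.6% |
| 0.2 SD | 9.7% | 15.7% |
| 0.3 SD | 15.8% | 29.3% |
| 0.5 SD | 35.2% | 65.1% |

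At r = 0.5 the rates for 0.2, 0.3 and 0.5 SD are 8.8%, 13.6% and 29.3%.

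**The opposite direction.** The rejection rate depends only on the net mean change, so the same table shows masking. A true improvement of 0.5 SD would be detected 65.1% of the time at r = 0.82. If order improved the Day 1 score by 0.2 SD, the net change would be 0.5 − 0.2 = 0.3 SD and detection would fall to 29.3%. At r = 0.6 it would fall from 35.2% to 15.8%.

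**Between arms.** The unpaired test uses post-test scores, which do not contain the Day 1 shift. If change scores were compared instead, as Objective 2 might suggest, a shift s common to both arms would cancel: (change + s) − (change + s) = 0 when the true changes are equal.

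**The case against.** The strongest reply is that the mechanism is not shown. The protocol's statement on craving concerns stimuli tied to past alcohol use, and the cue study in its literature review used guided imagery. A readiness-to-change questionnaire is neither. The 24 URICA items speak of a problem; drinking and alcohol appear only in the title and instructions. This stands.

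The direction is also open. Items 20 and 24 concern struggle and recurrence, but items 2, 4, 8, 11, 18 and 23 have the patient rate statements about working on change, which might raise perceived coping. A reader might infer that the order makes both interventions look effective, or that positive within-arm results would be artefacts. The documents support neither inference.

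The large percentages depend on the assumed shift. At 0.05 to 0.1 SD the test stays at about 5–8%. The case for the VAS is weaker than for the AUQ: on Day 1 the AUQ, with its explicit drinking content, stands between the URICA and the VAS, and it may precede the VAS on the later days too.

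Reordering does not equalise everything. The record sheet labels the first visit as intake and Day 1 together, so an eligibility interview may precede the baseline scores on that day alone. The timing of the later scores relative to the session is unstated, and that mismatch could matter more. Both stated hypotheses are between-arm, where this issue causes no bias.

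Two replies carry less weight. The protocol calls the URICA a screening tool, but states no URICA entry threshold and gives it after allocation, so it need not come first. Reversal does place the craving items just before the URICA, but no URICA analysis is planned.

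**Conclusion.** The point holds as a difference in measurement conditions: the Day 1 AUQ and VAS follow a drinking-problem questionnaire, and the scheduled later ones do not. Any resulting shift, of unknown size and sign, would pass into the within-arm change in both arms.

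Under the assumptions above (n = 10, two-sided 5% level, no true change, r from 0.6 to 0.82), the rejection rate is about 6–8% for a shift of 0.1 SD, 10–16% for 0.2 SD and 35–65% for 0.5 SD. The documents cannot say which of these is realistic.

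The point is confined to Objective 1. It is a free improvement to the procedure and does not undermine the randomised comparison.

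**What to change.** Reword the Day 1 sentence in the Procedure section so that the AUQ comes first, then the VAS, then the URICA, all before the first session. In the same place, state that on Day 3 and Day 5 the AUQ and VAS are completed before that day's session, as on Day 1, if that is not already intended.

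The cost is a change of wording: the instruments, days and patient burden stay the same.

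The swap removes the URICA order effect only. Any effect of a same-day intake interview remains, and the report should still not attribute within-arm change to treatment, because there is no untreated arm.
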